1.6 Correlative Studies

Archived tumor samples from the most recent biopsy or surgery will be used to correlate expression of CD95 and other cellular proteins of interest with response to AR-42 and pazopanib exposure.

2 OBJECTIVES

2.1 Primary Objective

To determine the recommended phase 2 doses (RP2Ds) of AR-42 and pazopanib when given in combination

2.2 Secondary Objectives

- 2.2.1 To evaluate the safety and toxicity of AR-42 and pazopanib when given in combination
- 2.2.2 To explore the antitumor effects of the AR-42 and pazopanib treatment regimen in patients with advanced RCC or STS

2.3 Exploratory Objective

To correlate expression of CD95 and other cellular proteins of interest with response to AR-42 and pazopanib treatment

3 STUDY DESIGN

3.1 General Description

This study is a single-arm, open-label, phase 1 trial to determine the RP2Ds of AR-42 and pazopanib when given in combination to patients with advanced RCC or STS. Eligible patients will have recurrent, unresectable, or metastatic RCC or STS for which pazopanib is an appropriate therapy.

AR-42 will be taken orally once per day on 3 non-consecutive days each week during the first 3 weeks of each 4-week cycle. Pazopanib will be taken by mouth once daily continuously during each cycle.

A modified 3+3 dose-escalation design will be followed until the maximum tolerated doses (MTDs) have been determined. Additional patients will be enrolled until a total of 12 patients have been treated at the MTDs. The maximum number of patients needed is 51 with an expected sample size of 29-35 patients enrolled over a period of about 15-35 months.

Correlative studies will be conducted using samples of tumor that were archived following the most recent surgery or biopsy.

3.2 Primary Endpoint

RP2Ds for AR-42 and pazopanib that are the same as or less than the MTDs

3.3 Secondary Endpoints

- 3.3.1 AEs characterized and graded according to the National Cancer Institute Common Terminology Criteria for Adverse Events Version 4.0 (NCI CTCAE v4.0) to determine the safety and toxicity of the combination of AR-42 and pazopanib
- 3.3.2 Tumor response based on Response Evaluation Criteria in Solid Tumors Version 1.1 (RECIST v1.1)

3.4 Exploratory Endpoint

Expression of CD95 and other proteins of interest by immunohistochemical (IHC) analysis using archived tumor samples from the most recent diagnostic biopsy or surgery (performed before initiation of study treatment) correlated with response to study treatment

4 PATIENT SELECTION

4.1 Inclusion Criteria

A patient must meet all of the following inclusion criteria to be eligible for this study.

- 4.1.1 Recurrent, unresectable, or metastatic RCC or STS (any histologic type) for which pazopanib is an appropriate therapy
- 4.1.2 Measurable or evaluable disease by RECIST v1.1
- 4.1.3 Age \geq 18 years
- 4.1.4 Eastern Cooperative Oncology Group (ECOG) performance status of 0 or 1 (see Appendix 1)
- 4.1.5 Adequate bone marrow function as defined below:
 - Absolute neutrophil count (ANC) ≥ 1200/mm³
 - Platelets \geq 120,000/mm³
 - Hemoglobin ≥ 9.5 g/dL

- 4.1.6 Adequate renal function as defined below:
 - Creatinine ≤ 1.5 x upper limit of normal (ULN) for the laboratory or calculated or actual creatinine clearance ≥ 60 mL/min (see Appendix 2 for the Cockcroft-Gault formula for calculating creatinine clearance)
 - Proteinuria ≤ 2+ [100 mg/dL]) using a random urine sample or < 3.0 gm using a 24-hour sample)

Note: If urine sample indicates $\ge 2+$ [100 mg/dL]), a 24-hour urine sample must be collected and tested; urine protein in the 24-hour sample must be < 3.0 gm/24 hours.

- 4.1.7 Adequate hepatic function as defined below:
 - Total bilirubin $\leq 1.5 \text{ x}$ ULN for the laboratory

Note: Patients with known Gilbert's Syndrome are **not** eligible for this study (Section 4.2.10).

- Aspartate aminotransferase (AST) ≤ 2.5 x ULN for the laboratory
- Alanine aminotransferase (ALT) $\leq 2.5 \times \text{ULN}$ for the laboratory
- 4.1.8 Non-hematologic toxicities from previous cancer therapies resolved to \leq grade 1
- 4.1.9 International normalized ratio (INR) \leq 1.5
- 4.1.10 Activated partial thromboplastin time (aPTT) \leq 1.5 x ULN for the laboratory
- 4.1.11 Left ventricular ejection fraction (LVEF) assessment (eg, echocardiogram, MUGA scan, first-pass technique) performed within 3 months prior to initiation of study treatment indicates an LVEF of ≥ 50%
- 4.1.12 A woman of childbearing potential (WCBP), defined as a woman who is < 60 years of age and has not had a hysterectomy, must have a documented negative serum pregnancy test within 7 days prior to initiating study treatment
- 4.1.13 A WCBP and a male patient with a partner who is a WCBP must agree to use a medically accepted method for preventing pregnancy for the duration of study treatment and for 2 months following completion of study treatment
- 4.1.14 Ability to understand and willingness to sign the consent form

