10 MEASUREMENT OF EFFECT

10.1 Criteria for Tumor Response

Tumor response will be evaluated and recorded according to RECIST v1.1 (27)

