10.2 Imaging

Only imaging of the initial sites of disease is required at subsequent time points to provide tumor measurements for assessment of antitumor effect. Brain imaging after initiation of study therapy is only required for patients who have a history of brain metastasis.

The same type of imaging used at baseline should be used at each scheduled assessment which will be performed at the end of every other 4-week cycle (ie, approximately every 8 weeks). At the investigator's discretion, additional imaging may be performed when clinically indicated.

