13.6.3 Efficacy-Evaluable Population

Efficacy-evaluable patients are those who have received any doses of AR-42 and pazopanib in cycle 2 (regardless of the number of doses taken during cycle 1), and have had at least 1 imaging assessment of response after receiving study treatment.

For efficacy evaluation, patients are coded as having a response or not having a response as follows:

- Responders: Best response assessment is a PR or a CR (Section 10).
- Non-Responders: Best response assessment is stable disease or progressive disease; also included are patients who did not have assessment of tumor response at least once after initiation of study treatment or who were otherwise not evaluable for response.

The coding of patients as responders or non-responders will be made by the Sponsor-Investigator with the concurrence of the Biostatistician.

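### Patients without measurable disease stay in the response denominator although they can be responders only through CR, which dilutes the CR + PR rate if any enrol

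*Combined protocol and SAP*

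**What the plan says.** - **Entry (4.1.2).** The criterion is "Measurable or evaluable disease by RECIST v1.1". The second alternative has a function only if patients without a measurable lesion can enrol. The protocol does not define evaluable disease.
- **Objective and criteria (2.2.2, 10.1, 10.2).** The secondary objective is "To explore the antitumor effects of the AR-42 and pazopanib treatment regimen". Section 10.1 states "Tumor response will be evaluated and recorded according to RECIST v1.1", and the response categories themselves are not reproduced. Follow-up imaging in 10.2 serves "to provide tumor measurements for assessment of antitumor effect".
- **Denominator (13.6.3).** A patient is efficacy-evaluable after any cycle 2 dosing with both drugs and at least one imaging assessment on treatment. Measurable disease at baseline is not a condition.
- **Coding (13.6.3).** "Responders: Best response assessment is a PR or a CR". Non-responders are those with stable or progressive disease, those never assessed, and those "or who were otherwise not evaluable for response".
- **Use (13.4, 13.5).** The CR + PR rate is reported with a 95% CI, with no null rate or test. Clinical response is also the outcome in an ordinal and a logistic regression on each biomarker. Neither section names its analysis set or asks for a separate result in measurable disease.

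**The concern.** Eligibility and endpoint do not match. A patient may enter without a lesion that can be measured, yet one of the two routes to being a responder is a measured shrinkage. For that patient an improvement short of complete disappearance cannot be recorded as a PR. The patient still counts in the denominator.

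Two results are exposed. The CR + PR rate becomes a blend of the rate in measurable disease and a CR-only rate in the rest, so it depends on the case mix at entry as well as on drug activity. The biomarker regressions take as non-responders some patients whose disease may have improved. The ordinal model has a further gap, because 13.6.3 gives no category for a best response that is neither CR nor progression in a patient without target lesions.

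**Working it through.** **1. The plan's own sample size (13.2).** It reproduces, using n / (1 − 0.20) for the allowance for patients inevaluable for DLT.
- Maximum: 36 / 0.80 = 45, and 45 + 6 = 51.
- Likely, lower end: 4 × 4.5 = 18; 18 / 0.80 = 22.5, rounded up to 23; 23 + 6 = 29.
- Likely, upper end: 5 × 4.5 = 22.5, rounded up to 23; 23 / 0.80 = 28.75, rounded up to 29; 29 + 6 = 35.

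I use N = 29 to 35 below. The efficacy-evaluable set can be smaller.

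**2. Inputs for the dilution.**
- p, the CR + PR rate in measurable disease: the documents give no expected rate. For illustration I take the pazopanib PR rates in the background: 31% in RCC (1.2.1) and 6% in STS (1.2.2).
- m, the share of the efficacy-evaluable set without measurable disease: not in the documents. Assumed 5% to 30%.
- c, the CR rate in that share: assumed 0. As a sensitivity value, 1.2.1 reports one CR; 170 patients being 31% implies about 170 / 0.31 = 548 patients, so c is about 1 / 548 = 0.2%.
- That PR is unavailable without measurable lesions is assumed from RECIST v1.1. The documents adopt that standard without reproducing the rule.

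**3. Formula.** Reported rate = p(1 − m) + c·m. The shift is −m(p − c), which is negative whenever m > 0 and c < p, and zero when m = 0.

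**4. Results with c = 0.**

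| m (assumed) | p = 31% | p = 6% |
|---|---|---|
| 0% | 31.0% | 6.0% |
| 5% | 29.5% | 5.7% |
| 10% | 27.9% | 5.4% |
| 20% | 24.8% | 4.8% |
| 30% | 21.7% | 4.2% |

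With c = 0.2%, every entry changes by less than 0.1 point (at most 0.30 × 0.2% = 0.06 point).

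**5. Against sampling error.** Exact (Clopper-Pearson) 95% CIs; the plan names no method.
- 9/29 = 31.0%, CI 15.3% to 50.8%, half-width about 18 points.
- 11/35 = 31.4%, CI 16.9% to 49.3%, half-width about 16 points.
- 2/29 = 6.9%, CI 0.8% to 22.8%, half-width 11 points.
- 2/35 = 5.7%, CI 0.7% to 19.2%, half-width about 9 points.

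The largest shifts, 9.3 points at p = 31% and 1.8 points at p = 6%, lie inside these half-widths.

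**6. Effect of restricting the denominator.** Suppose 6 of 29 patients have no measurable lesion and 7 of the other 23 respond.
- All efficacy-evaluable: 7/29 = 24.1%, CI 10.3% to 43.5%, width 33.2 points.
- Measurable disease only: 7/23 = 30.4%, CI 13.2% to 52.9%, width 39.7 points.

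**The case against.** The strongest reply is that this is a choice of estimand. Section 13.6.3 deliberately counts patients who cannot be evaluated as non-responders, a conservative convention, and the rate in measurable disease has no special claim to be the true one. The share of affected patients is unknown. Eligibility requires recurrent, unresectable or metastatic disease, with contrast-enhanced baseline imaging, so the share could be near zero. Even 3 patients in 29 would cost less than one response at a 31% rate (3 × 0.31 = 0.93). Response is descriptive and secondary, and 13.5 already says that the biomarker analysis lacks power.

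Most of this stands, and it limits the point. It does not remove it. A confidence interval describes sampling error, whereas this shift runs one way whenever such patients enrol and their CR rate is below p. One patient is about 3 percentage points at this sample size (1/29 = 3.4%, 1/35 = 2.9%). The biomarker models may have only about 2 to 11 responders to work with (6% of 29 to 31% of 35). The estimand question is answered by reporting both rates.

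A reader might infer three stronger claims that the documents do not support.
- **That these patients are always non-responders.** CR counts as a response for any patient under 13.6.3, and nothing bars them from it.
- **That the bias has a known size.** No share is stated, so every figure above is conditional.
- **That a comparison with the pazopanib rates in Section 1.2 is compromised.** No such comparison is planned, and the documents do not say whether those trials required measurable disease.

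**Conclusion.** The point holds in a conditional form. Sections 4.1.2 and 13.6.3 together place patients without measurable disease in the response denominator while, on the RECIST v1.1 rule as assumed here, leaving them CR as the only route to a response. If any enrol and their CR rate is below the CR + PR rate in measurable disease, the reported rate is diluted: by 1.6 to 9.3 points at p = 31% and by 0.3 to 1.8 points at p = 6%, for assumed shares of 5% to 30%. If none enrol, there is no effect.

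The consequence is confined to the secondary response summary and the exploratory biomarker models. It would be wrong to read it as a flaw in the primary objective: the DLT rules, the MTD and RP2D determination and the sample size do not use response. It is worth correcting because the remedy is cheap and specific, not because a decision in this trial turns on it.

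**What to change.** Keep 4.1.2 as it is, since these patients still contribute to the DLT and safety assessments. Then, in 13.4, 13.5 and 13.6.3:

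1. Calculate the CR + PR rate and its 95% CI in efficacy-evaluable patients who have at least one RECIST v1.1 measurable lesion at baseline.
2. Report the rate in all efficacy-evaluable patients alongside it.
3. Fit the biomarker-response models in the measurable-disease set.
4. List evaluable-only patients separately, with best response recorded as CR, non-CR/non-PD or PD.
5. In the same edit, reconcile 13.6.3 with itself. The efficacy-evaluable set requires imaging on treatment, yet its non-responder group includes patients with no response assessment. State which of the two governs the denominator.

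No new data are needed, because Table 19 (footnote L) already requires baseline imaging of the chest, abdomen, pelvis and other suspected sites. The cost is a smaller denominator and a wider interval. In the example above the width grows from 33.2 to 39.7 points, which is not trivial and is a reason to show both rates. The biomarker models also lose the evaluable-only patients.

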4.2 Exclusion Criteria

A patient who meets any of the following exclusion criteria is not eligible to participate in this study.

- 4.2.1 Symptomatic or untreated brain metastasis
- 4.2.2 Leptomeningeal metastasis
- 4.2.3 Any investigational agent within 4 weeks prior to initiating study treatment

- 4.2.4 Previous therapy with pazopanib
- 4.2.5 Inability to swallow medication
- 4.2.6 Known or suspected malabsorption condition or obstruction
- 4.2.7 Contraindication to antiangiogenic agents, including:
 - Serious non-healing wound, non-healing ulcer, or bone fracture
 - Major surgical procedure or significant traumatic injury within 4 weeks prior to initiating study treatment; other surgical procedures within 2 weeks prior to initiating study treatment
 - Pulmonary hemorrhage/bleeding event ≥ grade 2 within 12 weeks prior to initiating study treatment
 - Any other hemorrhage/bleeding event ≥ grade 3 within 12 weeks prior to initiating study treatment
- 4.2.8 History of organ allograft including corneal transplant
- 4.2.9 Evidence of bleeding diathesis or coagulopathy
- 4.2.10 Documented Gilbert's Syndrome
- 4.2.11 Resting systolic blood pressure (BP) < 100 mmHg
- 4.2.12 Hypertension defined as systolic BP ≥ 140 mmHg **or** diastolic BP ≥ 90 mmHg despite optimal medical management
- 4.2.13 QTc interval > 450 ms on screening 12-lead electrocardiogram (ECG)
 - If baseline QTc on screening ECG meets exclusion criteria:
 - Check calcium, potassium, and magnesium serum levels.
 - Correct any identified hypocalcemia, hypokalemia, and/or hypomagnesemia and repeat ECG to confirm exclusion of patient due to prolonged QTc interval.
 - For patients with heart rate (HR) 60-100 bpm, manual read of QTc is not required.
 - For patients with a baseline HR < 60 bpm or > 100 bpm, manual read of the QT interval by a cardiologist is required, with Fridericia correction applied to determine QTc (ie, QTcF).
- 4.2.14 Active or clinically significant cardiac disease including any of the following:
 - Unstable angina (eg, anginal symptoms at rest) or onset of angina within 3 months prior to initiating study treatment
 - Myocardial infarction within 6 months prior to initiating study treatment
 - Cardiac arrhythmias currently requiring anti-arrhythmic therapy other than beta blockers

4.2.15 Any documented history of clinically significant thrombotic, embolic, venous, or arterial events, such as cerebrovascular accident, transient ischemic attack, deep vein thrombosis, or pulmonary embolism necessitating therapeutic anticoagulation within 6 months prior to initiating study treatment

Note: Patients with a tumor-associated thrombus of locally-involved vessels should not be excluded from participating in the study.

- 4.2.16 Active infection requiring treatment or chronic infection requiring suppressive therapy
- 4.2.17 Chronic or active hepatitis B or C infection requiring treatment with antiviral therapy
- 4.2.18 Pleural effusion or ascites that causes respiratory compromise (eg, ≥ grade 2 dyspnea)
- 4.2.19 Required ongoing treatment with other drugs thought to potentially have adverse interactions with either of the medications included in the study treatment; if such medications have been used, patients must have discontinued these agents at least 1 week prior to initiating study treatment. Examples include:
 - Strong CYP3A4 inhibitors and/or strong CYP3A4 inducers; the reference list of CYP isozymes and classification of strong, moderate, and weak interactions are available through the FDA website, Tables 5 and 6: http://www.fda.gov/Drugs/DevelopmentApprovalProcess/DevelopmentResource s/DrugInteractionsLabeling/ucm093664.htm
 - Strong inhibitors of P-glycoprotein (P-gp) and/or breast cancer resistance protein (BCRP); the reference list of strong inhibitors of P-gp and BCRP is available through the FDA website, Table 9: http://www.fda.gov/Drugs/DevelopmentApprovalProcess/DevelopmentResource s/DrugInteractionsLabeling/ucm093664.htm
 - Simvastatin and other HMG-CoA reductase inhibitors (ie, statins)
 - Drugs that raise gastric pH including proton pump inhibitors and H2-blockers Note: Short-acting antacids, in place of PPIs and H2-blockers, are permitted.
 - HDAC inhibitors
- 4.2.20 Pregnancy or breastfeeding
- 4.2.21 Medical, psychological, or social condition that, in the opinion of the investigator, may increase the patient's risk or limit the patient's adherence with study requirements

5 STUDY ENTRY AND WITHDRAWAL PROCEDURES

5.1 Study Entry Procedures

5.1.1 Required Pre-Registration Screening Tests and Procedures

Refer to the study calendar (Section $\underline{12}$) for the screening tests and procedures that are required prior to registration and/or treatment and for the timing of these events relative to the start of treatment.

5.1.2 Registration Process

To register a patient, the study team will provide the following items to the registrar at VCU Massey Cancer Center

- Completed registration cover sheet
- Completed, signed, and dated eligibility checklist
- Signed and dated consent form

The registrar will complete the registration process by assigning a study identification (ID) number and forwarding the "Confirmation of Registration" form to the registering study team.

Study treatment may not begin until the Confirmation of Registration assigning a study ID number has been received from the registrar. The registering study team will enter the patient's initial enrollment data (eg, demographics, consent, eligibility, on-study, treatment assignment) into the OnCore database within 24 hours of registration (before study treatment begins).

5.2 Study Withdrawal

A patient may decide to withdraw from study participation at any time. Patients must be withdrawn from the study when any of the following occurs:

- Unacceptable toxicity defined as toxicity that requires holding one or both of the study medications for more than 21 consecutive days
- Consent withdrawal for study treatment and study procedures
- If, in the investigator's opinion, continuation of the study requirements would be harmful to the patient's well-being
- Patient is lost to follow-up

The reason for and date associated with study withdrawal or removal from the study must be documented in the source documents and OnCore database.

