6.5 Duration of Therapy

Treatment will continue until any of the following occurs (also see information regarding study withdrawal in Section 5.2):

- Interruption in either of the study medications due to unresolved toxicity for a period of more than 21 consecutive days
- AE that requires discontinuation of **both** study medications (see Section 7)
- Disease progression
- Patient decision to discontinue study treatment
- Investigator determination that discontinuation is in the patient's best medical interest
- Withdrawal of study sponsor support

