6.13 Follow-Up Period

Patients who discontinue treatment **for any reason other than consent withdrawal** remain on study in follow-up status for a 30-day evaluation period following the last dose of both study medications. During this 30-day post-treatment period, resolution or stabilization of ongoing treatment-related AEs and evolution of new treatment-related AEs will be reported. Additionally, if the patient has not had tumor progression, tumor response assessments performed during this 30-day follow-up period will also be reported.

Patients are off the study at the end of the 30-day follow-up period or when subsequent anticancer therapy begins, whichever occurs first. The primary reason(s) for a patient's discontinuation of study treatment and the patient's follow-up status will be recorded in the source documents and the CRFs.

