7.4 General Instructions and Guidelines

- If treatment delays are required, the cycle may be extended to 5 weeks; however, all AR-42 doses must be taken during the first 4 weeks of the 5-week cycle. Any doses not given within the first 4 weeks of the extended cycle will be omitted.
- If one or both of the study medications are held due to toxicity, a **maximum of 3 consecutive weeks is permitted for recovery**. If recovery has not been sufficient to resume treatment 3 consecutive weeks after the decision to hold either or both of the study medications, both study medications must be discontinued.
- If AR-42 treatment must be interrupted for an AR-42-related toxicity, the patient should continue taking pazopanib unless dose modification instructions specifically indicate that pazopanib should be held or omitted.
- If pazopanib treatment must be interrupted due to a pazopanib-related toxicity, the patient should continue taking AR-42 unless dose modification instructions specifically indicate that AR-42 should be held or omitted..

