8.4 Time Period and Grade of AE Capture

All AEs regardless of grade will be recorded from the beginning of the study procedures through 30 days following the end of study treatment.

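### Section 5.2 takes patients off the study after a toxicity hold of more than 21 days, while Sections 6.13 and 8.4 still require 30 days of follow-up for them

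*Combined protocol and SAP*

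**What the plan says.** Section 5.2 (Study Withdrawal) begins "Patients must be withdrawn from the study when any of the following occurs". Its first trigger is "Unacceptable toxicity defined as toxicity that requires holding one or both of the study medications for more than 21 consecutive days". The other triggers are consent withdrawal, the investigator's view that continuing the study requirements would harm the patient, and loss to follow-up. The section asks for the reason and date of withdrawal or removal. It does not mention any further follow-up.

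The same toxicity event appears in two other places with a different consequence:

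- Section 6.5 (Duration of Therapy) lists "Interruption in either of the study medications due to unresolved toxicity for a period of more than 21 consecutive days" as a reason to end treatment, and refers the reader to 5.2 for study withdrawal.
- Section 7.4 says that if recovery is insufficient after three consecutive weeks, "both study medications must be discontinued". It says nothing about leaving the study.

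Follow-up after treatment is governed by two sections and a table:

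- Section 6.13: patients who stop treatment "for any reason other than consent withdrawal" are to "remain on study in follow-up status for a 30-day evaluation period following the last dose of both study medications". It also defines the end of participation: "Patients are off the study at the end of the 30-day follow-up period or when subsequent anticancer therapy begins, whichever occurs first".
- Section 8.4: "All AEs regardless of grade will be recorded from the beginning of the study procedures through 30 days following the end of study treatment".
- Table 20 schedules an end-of-treatment visit and an AE assessment at the end of the 30 days. Footnote D lets the team obtain the AE information by contacting the patient, family or other care providers if a visit is not possible.

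**The concern.** The protocol has two concepts, stopping treatment and leaving the study, and gives one event both consequences without saying which section prevails. A patient withdrawn under the toxicity bullet of 5.2 has neither completed 30 days nor started new anticancer therapy, so by the definition in 6.13 that patient is still on study.

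At stake is what 6.13 schedules for those 30 days: the course of ongoing treatment-related AEs, new treatment-related AEs, and response assessments in patients who have not progressed. If a site followed 5.2 as written, follow-up would end because of toxicity, so the missing safety data would not be missing at random. Disease progression is listed in 6.5 but not in 5.2, so a patient who stops for progression would go into the 30-day follow-up while one who stops for prolonged toxicity would not. Safety and toxicity are the first secondary objective (2.2.1). Under 6.7.4, overall tolerability can also lead to a recommended phase 2 dose (RP2D) below the maximum tolerated dose. The expected enrolment is only 29-35 patients (13.2).

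**Working it through.** The plan gives no figure to reproduce here. The check is a comparison of text plus one subtraction.

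**Is it the same event?** Yes. Sections 5.2 and 6.5 use the same trigger, a toxicity hold of either drug for more than 21 consecutive days, and 7.4 uses the same limit expressed as three weeks. Only the consequence differs: off study in 5.2, off treatment in 6.5 and 7.4.

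**Can 5.2 be read as meaning off treatment?** Not easily. Its title and lead-in concern the study. It places the toxicity bullet beside consent withdrawal and loss to follow-up, both of which do end participation.

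**Do other sections exempt these patients from follow-up?** No. The only exception in 6.13 is consent withdrawal. Section 8.4 states no exception.

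**How many follow-up days would a literal reading of 5.2 remove?** Let *h* be the days from the last dose of both drugs to withdrawal under 5.2. I read the last dose of both drugs as the later of the two last doses, which is the clock in 6.13. Then:

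days lost = max(0, 30 − *h*)

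- Both drugs held from the same day: the trigger needs more than 21 days, so *h* is at least 22, and days lost are at most 30 − 22 = 8. If withdrawal comes 30 or more days after the last dose, the loss is 0.
- One drug held, the other taken until the day of withdrawal: *h* = 0, and days lost = 30 − 0 = 30.
- In between, for example if the second drug was last taken 10 days before withdrawal: 30 − 10 = 20.

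The second case is not remote. Section 7.4 makes it the default that a patient whose toxicity is attributed to one drug continues the other, unless the modification tables say otherwise. Pazopanib is taken daily, so if it is the continued drug, *h* can be close to 0. AR-42 is taken three days a week with a rest week, so if it is the continued drug, *h* may be some days and the loss somewhat less than 30.

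The result uses the 6.13 clock. Section 8.4 counts from the end of study treatment, which the plan does not equate with the last dose.

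**The case against.** The strongest reply is that follow-up is already protected. Section 6.13 is the specific rule and makes one exception only. Section 8.4 requires AE recording through 30 days without exception, and Table 20 schedules the assessment and allows it by contact. Follow-up is lost only if a site reads the lead-in to 5.2 alone and passes over three explicit requirements. This part stands: the loss is a risk and not a certainty. It also shows that 5.2 is the outlier. It does not remove the contradiction, because nothing says which section governs.

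It can also be said that little reaches the RP2D or the response analysis. Dose-limiting toxicity is assessed in cycle 1 (6.7.1), and the qualifying toxicity and the hold are on record before 5.2 can apply. The final scan is already conditional on no progression, at least 8 weeks since the last assessment, and feasibility (Table 20, footnote O). This stands too. What is exposed is mainly the resolution of AEs and late AEs.

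Two stronger readings are tempting, and the documents do not support them.

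- A reader might infer that the patients with the worst toxicity lose follow-up. The trigger is the length of the hold, not the grade. Several grade 4 events end treatment directly without a 21-day hold (other toxicities possibly related to AR-42 in Table 5, hypertension in Table 7, ALT/AST in Table 8). The toxicity bullet does not catch these, while a prolonged lower-grade toxicity could meet it.
- A reader might apply the 24% discontinuation rate in Section 1.2.1 and obtain 0.24 × 29 = 7.0 to 0.24 × 35 = 8.4 patients. That rate covers all AE discontinuations on pazopanib alone in previously untreated renal cell carcinoma. It includes no AR-42 and no sarcoma patients, and it does not count holds of more than 21 days. It is neither an estimate nor a bound for this trial.

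**Conclusion.** The contradiction is real and should be corrected. For the same toxicity event, 5.2 ends study participation, 6.5 and 7.4 end treatment, and 6.13, 8.4 and Table 20 call for 30 days of post-treatment follow-up.

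Under a literal reading of 5.2, the loss per affected patient is at most about 8 of the 30 days if both drugs were held together, and up to 30 days if one was continued until withdrawal. These figures assume withdrawal no earlier than day 22 of the hold and the 6.13 clock. The number of patients affected cannot be estimated from the documents. The group concerned is patients with prolonged, treatment-ending toxicity.

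The bullet on investigator-judged harm raises a related but separate question. A reader might infer that it too should become a treatment-stopping rule only. The text does not support that: the bullet speaks of study requirements, which can include visits and procedures as well as drug.

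**What to change.** Reconcile Section 5.2 with 6.5, 6.13 and 8.4:

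1. Separate ending study treatment from leaving the study, and use the two terms consistently.
2. State in 5.2 that patients who meet the 21-day toxicity criterion enter the 30-day follow-up already required by 6.13, 8.4 and Table 20.
3. For the bullet on investigator-judged harm, keep the investigator's ability to stop burdensome study procedures, and state whether 30-day AE capture still applies, by contact under Table 20 footnote D if needed.
4. Use one start point for the 30 days in 6.13 and 8.4.

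The cost is an amendment of wording. The follow-up is already in the study calendar, so no visits or tests are added. No change to any dose, hold limit or treatment-stopping rule is implied.
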